8.3.3 Secondary outcome analysis

Secondary outcomes will assess change in participant-reported quality of life and psychological well-being. Data will be collected using the SF-36, Hospital Anxiety and Depression Scale (HADS), and EQ-5D-5L at baseline, post-intervention, and 3-, 6- and 12-month follow-ups. Descriptive statistics will summarise scores at each timepoint. Mean within-participant changes from baseline will be presented with 95 % confidence intervals and standardised effect estimates.

Qualitative data from midpoint interviews (week 4) and the post-intervention focus groups/interviews will also be analysed using Reflexive Thematic Analysis.

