5.5 Study intervention(s) and comparator(s)

5.5.1 Description of study intervention

The study intervention is OurPERSPECTIVE, a virtual, group-based survivorship course co-designed with women who have experienced endometrial cancer.

SPONSOR REFERENCE: 1097

OurPERSPECTIVE endometrial cancer survivorship Study

Protocol Version v1.0 14/10/2025

IRAS: 363748

The course will be facilitated by a gynaecology clinical nurse specialist who is part of the UHL direct clinical care team and will be known to the participants. The course will be delivered online via a secure videoconferencing platform (Microsoft Teams). The course will run for 6-8 consecutive weeks, with one session each week lasting approximately 60 minutes. There are 6 core modules for all participants and 2 additional modules (menopause and sexual function) that participants can chose to attend if they wish. Each session combines education, discussion, workbook activities and peer support, and covers the following modules: physical activity, sleep disturbance, body changes, tiredness, fear of recurrence, tiredness, menopause, and sexual disturbance.

At the start of the course, group rules will be established to create a safe and respectful environment. Each session will conclude with a short debrief to check wellbeing and provide closure. The specialist nurse who will be facilitating the course will be able to provide additional support to participants who become distressed or indicate that they need additional support during a session.

Attendance at each session will be recorded in the attendance log. The courses will aim to have 10 women per cohort, with 3 cohorts planned for the feasibility study.

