8.1 Sample size calculation

The sample size for this feasibility study is pragmatic and based on the anticipated recruitment rate within University Hospitals of Leicester NHS Trust. Approximately 30 participants will be enrolled.

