8.5 Adjusted analysis

Not applicable.

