8.7 Participant population

Analyses will include:

- Enrolled set: all participants who consent;
- Intervention set: all participants who attend at least one session;
- Feasibility analysis set: all participants providing evaluable data at each timepoint.

Given the single-arm design, all available data will be included in descriptive analyses, with adherence and withdrawals reported.

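### The 95% intervals for mean change take no account of delivery in three peer-support cohorts, and would be too narrow if changes are positively correlated within a cohort

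*Protocol*

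**What the plan says.** All references are to the Protocol.

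- **Delivery (5.5.1).** The course is given to groups: "The courses will aim to have 10 women per cohort, with 3 cohorts planned for the feasibility study". On content: "Each session combines education, discussion, workbook activities and peer support". The facilitator appears in the singular: "The specialist nurse who will be facilitating the course".
- **Sample size (8.1).** "Approximately 30 participants will be enrolled". The basis is practical: "The sample size for this feasibility study is pragmatic and based on the anticipated recruitment rate". No precision target, standard deviation or design effect is given.
- **Secondary analysis (8.3.3).** "Mean within-participant changes from baseline will be presented with 95 % confidence intervals and standardised effect estimates". No model or variance estimator is named. These are the only confidence intervals in the protocol; the primary analysis in 8.3.2 is purely descriptive.
- **Where cohort might have appeared.** Section 8.5 on adjusted analysis reads "Not applicable", and 8.9 on other statistical considerations carries the same entry. The example factors in 8.4 are participant characteristics and do not include cohort. Section 8.7 says: "Given the single-arm design, all available data will be included in descriptive analyses, with adherence and withdrawals reported".

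**The concern.** Women in the same cohort share sessions, discussion and peer support, and section 1 cites evidence on group-based, peer-supported programmes as the rationale. Influence between members is therefore part of how the course is meant to work, and their changes after the course may be correlated.

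Section 8.3.3 deals with the pairing within each woman by analysing change from baseline. Nothing deals with the grouping of women. If the changes in a cohort are positively correlated, 30 women carry less information than 30 independent women, and an ordinary paired interval looks more precise than it is. One unusually good or poor group could also drive the pooled mean without the reader seeing it. The secondary outcomes are meant to inform the design of the later randomised trial (section 2), so a reader could carry these effect estimates and intervals forward at face value.

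**Working it through.** **Inputs from the protocol.** k = 3 cohorts and m = 10 women per cohort (5.5.1); about 30 women in total (8.1); a 95% interval for mean within-participant change (8.3.3).

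**Assumed input.** The ICC of the change scores. The protocol gives none and none can be derived from it, so 0, 0.01, 0.05 and 0.10 are used to show the range.

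**Step 1: the plan's own figure.** 3 x 10 = 30, which matches 8.1. This is arithmetic only, because the sample size is pragmatic and there is no formula to reproduce.

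**Step 2: the ordinary paired interval**, in units of the SD of change:

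half-width = t(0.975, 29) / sqrt(30) = 2.045 / 5.477 = 0.373 SD.

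**Step 3: allow for cohort.**

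- Design effect: DE = 1 + (m - 1) x ICC = 1 + 9 x ICC
- Effective sample size: 30 / DE
- Factor by which the half-width should grow: sqrt(DE)

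Example at ICC 0.05: DE = 1 + 9 x 0.05 = 1.45; 30 / 1.45 = 20.7; sqrt(1.45) = 1.20; 0.373 x 1.204 = 0.450 SD (1.204 is the unrounded factor).

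**Step 4: actual coverage of the ordinary interval**, by simulation with a normal cohort effect (variance = ICC), a normal residual (variance = 1 - ICC) and a one-sample t interval on all 30 changes.

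| Assumed ICC | DE | Effective n | Factor | Half-width (SD) | Coverage of ordinary interval |
|---|---|---|---|---|---|
| 0 | 1.00 | 30.0 | 1.00 | 0.373 | 95% |
| 0.01 | 1.09 | 27.5 | 1.04 | 0.390 | 94% |
| 0.05 | 1.45 | 20.7 | 1.20 | 0.450 | 90% |
| 0.10 | 1.90 | 15.8 | 1.38 | 0.515 | 84% |

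**Step 5: fewer evaluable women.** Ten per cohort is an aim. With 8 evaluable women per cohort and ICC 0.05, DE = 1 + 7 x 0.05 = 1.35 and coverage is about 91%, so the shortfall is slightly smaller.

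**Step 6: can the data supply the correction?** Hardly, with three cohorts. A t interval on the three cohort means holds 95% coverage but has 2 degrees of freedom. Taking the SD as known, its half-width is 4.303 x sqrt(1 / 30) = 0.79 SD at ICC 0 and 4.303 x sqrt(1.45 / 30) = 0.95 SD at ICC 0.05, more than twice the ordinary interval. A fixed cohort effect would not widen the interval for clustering.

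**Step 7: would one fixed ICC serve as the main analysis?** If the half-width is always inflated by sqrt(1.45), non-coverage is 2.0% at a true ICC of 0, 2.6% at 0.01, 5.2% at 0.05 and 9.0% at 0.10. It is right only when the guess is right, which favours showing a range.

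**The case against.** **The protocol does not say that the women are pooled as independent.** This stands: pooling is inferred. Section 8.5 may mean only that no covariates are adjusted for, and the list in 8.4 is open and concerns baseline characteristics, which delivery cohort is not. A separate statistical analysis plan might also specify the interval. However, section 8.3 is itself headed as the statistical analysis plan, and 8.9, where clustering would belong, is closed as not applicable. An ordinary paired interval is what someone following this text would compute.

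**A reader might infer that the intervals are in fact too narrow.** The documents do not support that. It needs a positive ICC, which the protocol neither gives nor implies. At ICC 0 the interval is correct and at 0.01 the loss is trivial. If one nurse leads every cohort, as the singular wording suggests, facilitator differences add nothing between cohorts. Peer-group effects could remain, so the possibility is real but its size is unknown. The protocol also does not say whether cohort membership is fixed.

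**A reader might infer that a decision about the later trial hangs on these intervals.** No section says so. The study summary ties progression to recruitment, retention, attendance and participant evaluation. The secondary outcomes are called exploratory, and their stated use is to show which measures suit the later trial. Section 8.3.2 rules out formal hypothesis testing for the primary outcomes. This stands, and it limits the weight of the point.

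**Any correction rests on a guessed ICC.** This also stands, and is why the inflated intervals belong in a sensitivity analysis.

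**Conclusion.** The point holds in conditional form and is minor. The protocol plans group delivery in three cohorts of about 10 and promises 95% intervals for mean change with no account of cohort. Read naturally, those intervals assume that women in the same cohort respond independently. Over assumed ICCs from 0 to 0.10, true coverage runs from 95% down to about 84%, and the half-width needed runs from 1.00 to 1.38 times the ordinary one. These figures rest on 3 x 10 evaluable women, normal cohort effects and ICCs that are assumed throughout. The protocol does not establish that the intervals will under-cover, but it does leave an assumption unstated that its own mode of delivery puts in doubt.

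**What to change.** - **Section 8.3.3:** keep the paired 95% interval, and label it as assuming independence between women in the same cohort.
- **Section 8.3.3:** add sensitivity intervals with the standard error multiplied by sqrt(1 + (m - 1) x ICC) at ICC 0.01, 0.05 and 0.10, where m is the evaluable number per cohort. State that these ICCs are assumptions.
- **Results tables:** show mean change, retention and attendance for each cohort beside the pooled figures.
- **Section 8.9:** replace the present entry with this rule.

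The cost is a few sentences and some extra table columns. Cohort can be read from the session attendance logs, so no new data are needed. The downside is that the sensitivity intervals are wider, by 4%, 20% and 38% with 10 evaluable women per cohort, and rest on assumed ICCs because three cohorts cannot estimate one reliably.

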8.4 Subgroup analyses

Feasibility outcomes and participant-reported changes will be examined by baseline characteristics such as ethnicity, deprivation quintile, time since treatment completion, and menopause status.

SPONSOR REFERENCE: 1097

OurPERSPECTIVE endometrial cancer survivorship Study

Protocol Version v1.0 14/10/2025

IRAS: 363748

8.5 Adjusted analysis

Not applicable.

8.6 Interim analysis and criteria for the premature termination of the study

No interim efficacy analysis is planned. Feasibility progress will be reviewed periodically by the Chief Investigator and Sponsor.

8.7 Participant population

Analyses will include:

- Enrolled set: all participants who consent;
- Intervention set: all participants who attend at least one session;
- Feasibility analysis set: all participants providing evaluable data at each timepoint.

Given the single-arm design, all available data will be included in descriptive analyses, with adherence and withdrawals reported.

8.8 Procedure(s) to account for missing or spurious data

Not applicable

8.9 Other statistical considerations.

Not applicable

[figure not shown]
8.10 Economic evaluation

Not applicable

9 Data Management

Not applicable

9.1 Data flow diagram (this is a mandatory requirement)

9.2 National data opt-out (this section is mandatory)

The national data opt-out was introduced on 25th May 2018 enabling patients to opt out from the use of their data for research or planning purposes in line with the recommendations of the National Data Guardian in their review of Data Security, Consent and Opt-outs. As from 1st August 2022, all NHS Trusts are now compliant with the national data opt-out operational policy guidance document; for further information please visit <https://digital.nhs.uk/services/national-data-opt-out/operational-policy-guidance-document>. The NHS Trust's R&I SOP for the national opt-out will be adhered to before patients are approached/invited and before any data processing takes place.

9.3 Source data

Source documents are defined as the first place where study data are recorded, from which entries into the case report forms (CRFs) are derived. For this study, source documents will include:

- Hospital records (used to confirm eligibility, diagnosis, and treatment completion date)

SPONSOR REFERENCE: 1097

Our PERSPECTIVE endometrial cancer survivorship Study

Protocol Version v1.0 14/10/2025

IRAS: 363748

- Signed informed consent forms
- Participant-reported questionnaire responses (completed electronically or on paper)
- Participant reflective diaries
- Attendance logs for the OurPERSPECTIVE sessions
- Audio recordings and anonymised transcripts of focus groups

CRF entries will themselves constitute source data when they are the original record, for example, attendance records or direct questionnaire data entered electronically.

All documents will be stored securely and under confidential conditions. On all study-specific documents, other than the signed consent form, participants will be identified only by their unique study ID number rather than by name.

9.4 Data collection tools, handling and record keeping

Each participant will be assigned a unique study identification number upon consent. This identifier will be used on all study-specific documentation and data collection tools in place of the participant's name.

Study data will be collected primarily through participant-completed questionnaires (baseline, midpoint, post-intervention) and attendance logs for the OurPERSPECTIVE course. Data will first be captured in paper case report forms (CRFs) or electronic questionnaire booklets and subsequently entered into a secure University of Leicester research database. The database will be hosted on encrypted University servers located within the UK. Access will be limited to authorised members of the research team using individual usernames and passwords.

Signed informed consent forms will be retained in the Site File (SF) with the clinical research team (located in the Gynaecology Research Office at Leicester General Hospital), with a copy also placed in each participant's NHS medical notes. All SF documents will be stored securely in a locked cabinet within a locked office within University Hospitals of Leicester NHS Trust.

To maximise completeness of data, reminders will be sent to participants who do not return questionnaires within the expected timeframe. These reminders will be issued by email or telephone, with follow-up by post if required. Participants who withdraw will be asked whether they are willing to complete an early-exit questionnaire, and partial data collected prior to withdrawal will be retained with consent.

Participant contact details will be held separately from research data in a password-protected file accessible only to the research team. This contacts database will be stored on the University of Leicester secure server, in compliance with GDPR and NHS data protection requirements.

SPONSOR REFERENCE: 1097

OurPERSPECTIVE endometrial cancer survivorship Study

Protocol Version v1.0 14/10/2025

IRAS: 363748

All electronic systems will comply with Good Clinical Practice (GCP) standards:

- The database will maintain an audit trail of data changes, with no capacity for deletion of original entries.
- Data entry rights will be restricted to authorised study personnel.
- Regular backups will be performed in line with University IT policies.
- An unambiguous participant identification code will allow linkage of all data collected for each participant.
- Pseudonymisation will be maintained at all stages, and only anonymised data will be shared outside the Sponsor institution.

All study documentation containing identifiable data will be managed in accordance with ICH-GCP, the UK Policy Framework for Health and Social Care Research, GDPR, and the Data Protection Act. Documents will be retained securely for at least six years after study closure, after which secure destruction will be arranged.

9.5 Access to data

The Chief Investigator and authorised members of the study team will have access to data collected as part of this research. Access to the study database will be restricted through role-based permissions, ensuring that only personnel with appropriate responsibilities can view or edit data. All members of the study team will be suitably trained prior to being granted access. Individual user accounts will be password-protected and will not be shared between members of the team.

Direct access to source data and study documentation will also be granted to authorised representatives from the Sponsor (University of Leicester), the host institution (University Hospitals of Leicester NHS Trust), and regulatory authorities, for the purposes of monitoring, audit, and inspection. Such access will be in line with participant consent and applicable data protection regulations.

9.6 Archiving

All study data and essential documents will be archived for a minimum of six years after study closure, in line with University of Leicester and NHS Trust policy. Paper records will be stored securely on site, and electronic data will be retained on encrypted University servers with restricted access. Archiving will follow the University of Leicester Archiving SOP (<https://le.ac.uk/research/regi/standard-operating-procedures>). Destruction of documents will require formal Sponsor authorisation.

10 Quality Assurance Procedures

The study will be conducted in accordance with the current approved protocol, ICH-GCP, the principles of the Declaration of Helsinki, and all relevant regulations and standard operating procedures (SOPs). The Principal Investigator, or their delegate,

SPONSOR REFERENCE: 1097

OurPERSPECTIVE endometrial cancer survivorship Study

Protocol Version v1.0 14/10/2025

IRAS: 363748

will be responsible for maintaining the Investigator Site File and ensuring it is kept “inspection ready” at all times.

10.1 Monitoring, audit and inspection

The University of Leicester as Sponsor operates a risk-based monitoring programme which this study will be subject to.

11 Protocol Compliance

11.1 Protocol deviations

A study related deviation is a departure from the ethically approved study protocol or other study document or process (e.g. consent process or administration of study intervention) or from Good Clinical Practice (GCP) or any applicable regulatory requirements. Planned deviations or waivers are not allowed however it is acknowledged that accidental protocol deviations may occur. Any deviations from the protocol will be documented in a protocol deviation form and filed in the Trial Master File/Investigator Site File as applicable.

If a protocol deviation occurs, then the CI (or delegate) will document this in accordance with the University’s Standard Operational Procedure (SOP) Identifying and Reporting Deviations and Serious Breaches of GCP and/or the Protocol.

Deviations from the protocol which are found to frequently recur will be explored and where necessary an amendment to the protocol will be made.

11.2 Serious breaches

A “serious breach” is a breach of the protocol or of the conditions or principles of Good Clinical Practice which is likely to affect to a significant degree –

- (a) the safety or physical or mental integrity of the trial subjects; or
- (b) the scientific value of the research.

In the event that a serious breach is suspected the Sponsor will be contacted within one working day. In collaboration with the CI, the serious breach will be reviewed by the Sponsor and, if appropriate, the Sponsor will report it to the approving REC committee and the relevant NHS host organisation within seven calendar days.

12 Ethical and Regulatory Considerations

12.1 Research ethics committee (REC) and regulatory review, approvals/permission/support, compliance and reports

Once the Sponsor Review process is complete, authorisation from the University of Leicester’s Research Governance Office will be issued to book further regulatory review of the proposed research. The University of Leicester’s Ethics Committee will then review the proposal. Agreement in principle is subject to the research receiving all relevant regulatory permissions. Submission for regulatory approvals will occur via the Integrated Research Application System (IRAS). The Chief Investigator will ensure that all regulatory approvals,

SPONSOR REFERENCE: 1097

OurPERSPECTIVE endometrial cancer survivorship Study

Protocol Version v1.0 14/10/2025

IRAS: 363748

confirmation of capacity and capability from NHS sites and sponsor green light are in place before participants are approached.

For any required amendment(s) to the study, amendment will be submitted to the sponsor in the first instance for review and approval to submit the amendment for external regulatory approval. Amendments must be implemented following all required ethical, competent authority, site and Sponsor approvals and in line with Sponsor Standard Operating Procedures.

The Research Governance Office's Standard Operating Procedures will be followed for the duration of the study.

The Chief Investigator will notify the REC when the study has ended by completing the end of study notification form and will submit a final report of the results within one year after notifying REC.

A Trial Master File and an Investigator Site File (per site) will be maintained for the duration of the study and will be stored for a minimum of 6 years after the study has ended. The only time this could be exceeded, is if samples are being retained beyond the scope of the original study i.e. there is consent for future research. In this circumstance ICFs may be retained for as long as the samples are in existence, as we have a legal requirement to prove the samples were obtained with consent.

12.2 Peer review

This study has undergone peer review by senior oncology and gynaecology specialist nurses who are leading such survivorship initiatives and are experts in gynaecological cancers. The review was proportionate to the size and complexity of the study, which is a single-centre, low-risk feasibility study.

The review process considered the clinical relevance, feasibility of recruitment and delivery within the NHS, and the methodological appropriateness of the design. Feedback was incorporated into the final version of the protocol to ensure clarity, feasibility, and compliance with NHS research governance standards.

As this is a small-scale feasibility study and not seeking adoption onto the NIHR CRN Portfolio at this stage, peer review by expert nurses who would be delivering or overseeing such an intervention was deemed sufficient. The review is consistent with the requirement for proportionality in peer review standards, ensuring the protocol is appropriate for submission and delivery within the host institution.

